**Treatment regimen:** The number of acupuncture treatments was set at up to five treatments in the one-week study period (treatments was not provided on weekends) or until the patient is delirium-free for 48 hours. Each session lasted 15-20 minutes.

**Other components of treatment:** Patients of acupuncture group also received SOC. Prior to the start of the study, a multicomponent protocol for delirium management was developed and implemented in internal medicine departments. This protocol was based on best literature evidence, current practice guidelines and the opinions of geriatric and psychiatric consultants, and included both pharmacological and non-pharmacologic interventions as published in a preceding manuscript. All clinicians working in the internal medicine departments were educated regarding the protocol and its use. This protocol was defined “SOC” for the study. Since the actual care of patients may differ according to clinical data and physician consideration, the use of psychotropic drugs (including antipsychotics) during hospitalization were documented and compared between the study arms. No other complementary medicine therapies other than acupuncture were added. Explanations were given to patients and their next-of-kin on potential benefits and side effects of acupuncture and treatment was administered only after they signed informed consent.

**Practitioner background:** The treatment was administered by seven acupuncturists with at least 5 years of clinical experience in a hospital setting.

**Control intervention:** In the control group, patients received SOC only.

**Outcomes:** All daily outcomes were collected daily for one week after randomization or until the patient was discharged from the hospital.

Primary outcome: Our primary endpoint was resolution of delirium during the 7 days of evaluation and was measured as time-to-first remission of delirium and number of delirium-free days, based on daily assessment of CAM scale.

Secondary outcomes:

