**Sample size calculation:** Since no previous study has evaluated an acupuncture-based intervention in older adults with delirium, a pilot study of 32 patients [acupuncture group (n=24); control group (n=8)] was designed to estimate accurately the sample size for our current study. In the pilot study, delirium-free days were  $3.2 \pm 1.6$  in the acupuncture group as compared with  $1.7 \pm 2.4$  in the control group. Taking into account a Type I error (alpha) of 0.05, a power of 0.80, pairwise comparison between our two study arms, and using G\*Power 3.1.9.4 software, we calculated a minimal sample size of 28 patients in each of the 2 study arms.

**Randomization:** Patients were randomized in two groups by convenience allocation according to acupuncturists' working days: patients with delirium diagnosed on Sunday, Monday, Wednesday or Thursday were assigned to the acupuncture arm, while patients with delirium diagnosed on Tuesday, Friday or Saturday were assigned to SOC arm. Blinding was clearly not feasible.

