**Statistical methods:** Demographic and clinical data was analyzed at baseline to measure the balance among the study groups. Quantitative variables were described using mean and standard deviation or median with range (minimum and maximum) depending on their distribution. Qualitative variables were described using frequency and percentage distributions. Next, we showed that our variables distribute equally between the two groups. For comparing normally distributed variables between our study groups, we used the t-test for independent samples. For comparing variables that do not distribute normally between our study groups, we used the Mann-Whitney test. For comparing qualitative variables between our study groups, we used the independent Chi-square test and Fisher exact test. Time-to-first delirium remission was evaluated using the Kaplan-Meier product limit survival estimator with log-rank between-group comparison and Cox regression was performed for multivariate adjustment of potential confounders. Hazard ratio (HR) with confidence intervals (CI) was calculated for each independent variable and controlled for all other independent variables in the regression. Patients who died or were discharged before day 7 had all subsequent days counted as the last day of evaluation in terms of both CAM and CAM-S. Intention-to-treat (ITT) analysis was planned to provide more information on the effect of the intervention. We explored the variables for possible collinearities, interaction, and confounders. All comparisons were two-sided with

significance level set at  $p<0.05$ . Data analysis was performed using IBM SPSS version 22 statistics software.

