## **RESULTS:**

Baseline patient data: Overall, 132 patients were screened for eligibility. Among them, 81 were recruited – 50 to the acupuncture arm and 31 to the SOC arm. Baseline sociodemographic and medical characteristics were similar in the two study arms as shown in Table 1. To note, all the patients randomized to the acupuncture arm were treated with acupuncture, while no patient assigned to the SOC arm received acupuncture (Fig. 1), so the planned ITT analysis was not required. In the acupuncture arm, 14 (28%) were censored (dead/discharged in the 7 days of follow-up), as compared with 8 (26%) in the SOC arm ( $p=0.87$ ). No difference in the baseline characteristics was noted between censored patients and patients completing the 7 days of follow-up.

Primary endpoint: Time-to-first delirium remission was shorter in the acupuncture arm as compared to the SOC arm ( $p<0.001$  for log-rank comparison, Fig. 2A). In the 7 days of evaluation, we calculated a number needed to treat (NNT) of 3 for first delirium remission. A multivariate Cox regression analysis was also conducted to evaluate the association of study arm allocation with the primary outcome (time-to-first delirium remission), adjusted for potential sociodemographic and medical confounders (age, gender, APACHE-II score, Charlson comorbidity index, number of psychotropic drugs, mobilization, cognitive impairment, reason for admission and type of delirium). The analysis showed that after adjusting for potential confounders, the time-to-first remission of delirium in the acupuncture arm was significantly shorter than in the SOC arm [HR 0.267 (95% CI 0.098-0.726,  $p=0.010$ ), Fig. 2B], while HR of potential confounders were not statistically significant. This means that acupuncture associated with SOC significantly increased the incidence of delirium remission by about 4-times, as compared to SOC only, after adjusting for sociodemographic and medical characteristics (model significance:  $p=0.042$ ). Furthermore, in the 7 days of evaluation, a significantly higher number of delirium-free days was found in the acupuncture arm [median 5.5 (0-6)] as compared with the SOC arm [median 0 (0-6)],  $p<0.001$ . Based on these results, the power of the study was calculated as 100%.

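### The 100% power figure is computed from the observed results, and delirium-free days, a primary measure and the basis of the sample size, have no between-arm estimate or confidence interval

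*Combined protocol and SAP*

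**What the plan says.** Methods, Outcomes defines the primary endpoint as resolution of delirium, "measured as time-to-first remission of delirium and number of delirium-free days, based on daily assessment of CAM scale".

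Methods, Sample size calculation sizes the trial on the second measure. The pilot gave 3.2 ± 1.6 delirium-free days with acupuncture (n=24) and 1.7 ± 2.4 with control (n=8). "Taking into account a Type I error (alpha) of 0.05, a power of 0.80, pairwise comparison between our two study arms", this led to 28 patients per arm. The trial recruited "50 to the acupuncture arm and 31 to the SOC arm".

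Methods, Statistical methods says "For comparing variables that do not distribute normally between our study groups, we used the Mann-Whitney test". It plans no power calculation from the results.

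Results, Primary endpoint gives time to first remission an adjusted hazard ratio of 0.267 (95% CI 0.098 to 0.726) and a number needed to treat (NNT) of 3. For the other measure it reports a significant advantage in these terms: "number of delirium-free days was found in the acupuncture arm [median 5.5 (0-6)] as compared with the SOC arm [median 0 (0-6", with a p-value below 0.001. The next sentence is "Based on these results, the power of the study was calculated as 100" per cent.

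**The concern.** There are two linked gaps in reporting.

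First, a reader will take the power of the study to be a property of its design. By the sentence's own wording, the figure comes from the data just analysed. No test, effect or SD is given for it, and it tells the reader nothing that p<0.001 has not already said.

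Second, after a significant result the reader needs the size of the difference and its precision. Time to remission has both. Delirium-free days have neither, although the trial was planned around a mean difference of 1.5 of them. Table 1 covers baseline only, and by their captions Figures 2 and 3 show time to remission and severity, so the estimate is not given elsewhere. What is at stake is what can be concluded about the size of the benefit, not whether a difference was found.

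**Working it through.** **1. Reproduce the planned sample size.** Inputs from Sample size calculation: difference 3.2 − 1.7 = 1.5 days, SDs 1.6 and 2.4, alpha 0.05, power 0.80. Two-sided testing comes from Statistical methods. With the simple average SD, (1.6 + 2.4)/2 = 2.0:

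n per arm = 2 × (1.960 + 0.842)² × 2.0² / 1.5² = 27.9, which rounds up to 28.

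This matches the plan. By the same formula the root-mean-square SD, √((1.6² + 2.4²)/2) = 2.04, gives 30, and the SD weighted by pilot arm size, √((23 × 1.6² + 7 × 2.4²)/30) = 1.82, gives 24. SD 2.0 is therefore the natural planning value.

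**2. Power at 50 and 31 for the planned difference.** Noncentral t, 79 degrees of freedom, noncentrality (1.5/SD) × √(50 × 31/81) = (1.5/SD) × 4.374. With SD 2.0 this is 3.28.

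| SD assumed | Power |
|---|---|
| 2.0 (reproduces 28 per arm) | 90% |
| 2.04 (root mean square) | 89% |
| 1.82 (weighted by pilot size) | 95% |
| 2.4 in both arms | 77% |
| 1.6 in both arms | 98% |

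**3. What observed power adds.** To a normal approximation it is Φ(z − 1.96), where z belongs to the two-sided p-value. So p=0.05 gives 50%, p=0.010 gives 73% and p=0.001 gives 91%. A p-value of about 5.7 × 10⁻⁶ or less is needed to round to 100%. The figure is a re-expression of p.

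**4. What the printed summary says about the mean difference.** This is illustration only. Assumptions: whole days, all 50 and 31 patients analysed, and a Mann-Whitney p-value (tie-corrected normal approximation).

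- *Acupuncture.* A median of 5.5 with n=50 puts the 25th and 26th ordered values at 5 and 6. There are then 25 sixes, at least one five and, from the range, at least one zero. The mean lies between 155/50 = 3.10 and 270/50 = 5.40.
- *SOC.* A median of 0 with n=31 needs at least 16 zeros, and the range needs at least one six. The mean lies between 6/31 = 0.19 and 90/31 = 2.90.
- *Medians and ranges alone.* The difference lies between 3.10 − 2.90 = 0.20 and 5.40 − 0.19 = 5.21.
- *Adding p<0.001.* Enumerating all count patterns raises the minimum to 177/50 − 80/31 = 0.96. The maximum stays at 5.21.

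Other printed results narrow this.

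- *Upper end.* The 5.21 pattern has 49 of 50 and 1 of 31 patients with any delirium-free day, a risk difference of 0.98 − 0.03 = 0.95 and so an NNT of about 1. If the printed NNT of 3 counts such patients and was rounded up, the risk difference is below 0.5. The largest case is then 49/50 − 15/31 = 0.496, with means 270/50 = 5.40 and 20/31 = 0.65, a difference of 4.75. If the NNT was rounded to nearest, the risk difference is at most 0.40. The largest case is then 44/50 − 15/31 = 0.396, with means 245/50 = 4.90 and 0.65, a difference of 4.25.
- *Lower end.* The 0.96 pattern gives 15 SOC patients 5 or 6 delirium-free days. The Results on delirium severity place 24 of 28 SOC patients in the high category, so at most 4 listed plus 3 unlisted patients, 7 in all, were outside it. Allowing at most 7 SOC patients with 5 or 6 free days raises the minimum to 178/50 − 73/31 = 1.21. Allowing at most 7 with 4 to 6 free days raises it to 178/50 − 65/31 = 1.46.

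The narrowed range therefore starts at roughly 1.2 to 1.5 days and ends at roughly 4.3 to 4.8 days.

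**The case against.** The strongest reply is that the report follows its own plan. Statistical methods calls for medians with ranges and a Mann-Whitney test for non-normal variables, and promises confidence intervals only for hazard ratios. Both arm medians are printed, and the other primary measure has a hazard ratio with its interval and an NNT. A mean is also an awkward summary of a variable bounded at 0 and 6 with medians of 5.5 and 0. This stands in part: the leading estimate should match the Mann-Whitney test. It does not remove the gap, because arm medians carry no precision for the comparison and the sample size rests on a mean difference.

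A second reply is that a range of 0.96 to 5.21 days overstates the uncertainty. That is right. It ignores the printed NNT and severity counts, which fit the two extremes poorly. The narrowed range is itself conditional: the NNT may have been read off the Kaplan-Meier curve, and the severity cut-offs are not printed, so the low-end caps are a judgement of plausibility.

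Stronger readings that a reader might infer are not supported:

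- *The trial was underpowered.* At SD 2.0 the power is about 90%. Only a single SD of 2.4 in both arms brings it below 80%.
- *The 100% is arithmetically wrong.* A very small p-value would give it, and only p<0.001 is printed.
- *The primary endpoint has no confidence interval at all.* Time to remission has one.
- *The gain is 5.5 days, from subtracting medians.* The documents do not report this as an effect, and it is not the mean difference used for planning.
- *The true gain may be near zero.* The constructed patterns are not estimates of the trial result, and an interval computed from one of them should not be quoted.

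**Conclusion.** Both parts hold as points of reporting. The 100% is power computed after the fact. The design figure for 1.5 days at 50 and 31 patients is about 90%, on the assumption of a two-sided t-test at 0.05 with SD 2.0, and it moves between 77% and 98% with the SD chosen. Delirium-free days lack a between-arm estimate with an interval. The printed results leave room for a mean gain from about the planned 1.5 days, or slightly less, to roughly three times it (4.25/1.5 = 2.8; 4.75/1.5 = 3.2), under the assumptions stated with the bounds. The actual value needs patient-level data. The finding of a difference, the tests and the p-values are unaffected.

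**What to change.** Delete the 100% sentence. If a power statement is wanted, replace it with: *For the pilot difference of 1.5 days, 50 and 31 patients give about 90% power (two-sided 0.05, t-test, SD 2.0).*

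Beside the medians already given, add:

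- a Mann-Whitney-based estimate with 95% CI: the probability that an acupuncture patient has more delirium-free days than an SOC patient (ties counted as one half), or the Hodges-Lehmann shift;
- the two arm means and their difference, with a bootstrap 95% CI, set against the planned 1.5 days.

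The cost is one sentence removed or replaced and two estimates computed from data already held. The power figure becomes less favourable. No patients are added, and no reported test or p-value changes.

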## Secondary endpoints:

*Delirium severity:* The long CAM-S sum from day 2 to day 7 of evaluation was significantly lower in the acupuncture group [11 (24%) with no delirium, 6 (13%) with low severity, 9 (20%) with moderate severity and 19 (42%) with high severity] as compared with the control group

[3 (11%) with no delirium, 0 with low severity, 1 (4%) with moderate severity and 24 (86%) with high severity], p=0.002, Fig. 3.

*Number of psychotropic drugs-free days:* The number of psychotropic drugs-free days in the 7 days of evaluation was similar in the two study groups [median: 7 (0-7) in acupuncture arm vs 7 (0-7) in SOC arm, p=0.253].

*Pain:* No difference in daily evaluation of pain intensity was found between the two study arms in the 7 days of evaluation.

*Sleep:* According to the tenth CAM-S item daily evaluation, no difference was found in terms of quality of sleep between the study arms during the 7 days of evaluation.

*Delirium complications:* No difference was found in terms of delirium-related complications between the study arms [median: 0 (0-6) complications in acupuncture arm vs 0 (0-1) complications in SOC arm, p=0.665].

*Length of hospitalization:* The duration of hospitalization was similar in the 2 study arms [median: 13 (2-67) days in the acupuncture arm vs 12 (2-54) in the SOC arm, p=0.945].

*Functional status at discharge:* Katz ADL at discharge was similar in the two study arms [median: 2 (0-6) in the acupuncture arm vs 3.5 (0-6) in the SOC arm, p=0.945].

*Safety:* No safety event was reported according to daily AcupAE evaluation.

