## Tables and figures:

[figure not shown]
Table 1: Baseline characteristics

Baseline characteristics		Acupuncture + SOC (n=50)	SOC only (n=31)	p
Male gender – N (%)		25 (50%)	19 (61%)	0.36
Age (years) – Mean (SD)		84.0 (7.8)	85.3 (6.7)	0.45
Prevalent delirium – N (%)		26 (52%)	16 (52%)	1.00
APACHE-II – Median (min-max)		9 (5-22)	11 (6-19)	0.31
Number of medications – Median (min-max)		8 (0-16)	9 (1-15)	0.38
Number of psychotropic drugs – Median (min-max)		1 (0-5)	1 (0-3)	0.66
Mobilization – N (%)	Normal	24 (48%)	9 (19%)	0.19
	Walking aid	15 (30%)	15 (48%)	
	Wheelchair	2 (4%)	3 (10%)	
	Bedridden	9 (18%)	4 (13%)	
IQCODE – N (%)	Normal cognitive status	28 (56%)	12 (39%)	0.35
	Mild dementia	17 (34%)	16 (52%)	
	Moderate dementia	4 (8%)	3 (10%)	
	Severe dementia	1 (2%)	0	
ADL – Median (min-max)		4.5 (0-6)	4 (0-6)	0.36
Reason for admission – N (%)	Infection	19 (38%)	12 (39%)	0.94
	Dyspnea	9 (18%)	9 (29%)	
	General Deterioration	8 (16%)	4 (13%)	
	Falls	3 (6%)	3 (10%)	
	Anemia	2 (4%)	1 (3%)	
	Other	9 (18%)	2 (6%)	
Delirium category – N (%)	Hyperactive	23 (46%)	12 (39%)	0.45
	Hypoactive	15 (30%)	12 (39%)	
	Mixed	9 (18%)	3 (10%)	
	Subsyndromal	3 (6%)	4 (13%)	
Hearing and/or visual impairment – N (%)		26 (52%)	22 (71%)	0.11
Charlson Comorbidity Index – Median (min-max)		7 (4-13)	7 (4-11)	0.97
Baseline delirium severity (Long CAM-S) – Median (min-max)		8 (3-15)	9 (4-14)	0.63

[figure not shown]
Legend: ADL: Activities of Daily Living; APACHE: Acute Physiology And Chronic Health Evaluation; CAM-S: Confusion Assessment Method Severity; SOC: Standard-of-care.

Figure 1: CONSORT Flow Diagram for non-pharmacologic interventions

Legend: SOC: Standard-of-care

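### The finding that psychotropic use during the trial was similar in the two arms rests on a measure at its ceiling and a non-significant test, with no estimate, interval or stated rule for patients who left early

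*Combined protocol and SAP*

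**What the plan says.** Under Other components of treatment, the Methods accept that actual care could vary with clinical data and physician judgement, and give this as the reason why "the use of psychotropic drugs (including antipsychotics) during hospitalization were documented and compared between the study arms". The Outcomes section lists the number of days on an antipsychotic, taken from daily chart review, as the second secondary outcome. It also says that daily outcomes were collected for one week or until discharge.

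The Results, under Secondary endpoints, report a different quantity: "The number of psychotropic drugs-free days in the 7 days of evaluation was similar in the two study groups", with "median: 7 (0-7) in acupuncture arm vs 7 (0-7) in SOC arm, p=0.253". No antipsychotic-day result appears.

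On follow-up, the Results report: "In the acupuncture arm, 14 (28%) were censored (dead/discharged in the 7 days of follow-up"), "as compared with 8 (26%) in the SOC arm". Under Statistical methods, patients who died or left before day 7 "had all subsequent days counted as the last day of evaluation in terms of both CAM and CAM-S". No rule is given for drug days.

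Table 1 has a baseline row, "Number of psychotropic drugs – Median (min-max"), with medians of 1 (0-5) and 1 (0-3), p=0.66. The Cox model includes a covariate with the same name.

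**The concern.** Arms were assigned by weekday of diagnosis and nobody was blinded, so equal co-treatment cannot be taken for granted. The document names psychotropic use as the thing to check. Such drugs can alter attention, arousal and agitation, which the CAM and CAM-S score. If use differed between arms, part of the difference in remission could come from background treatment.

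The drug-free-day line is the only comparison of drug use during the trial that is reported. It has three weaknesses:

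- Both medians are at the maximum of the scale, and similarity is inferred from a non-significant p-value.
- More than a quarter of patients were not observed for all 7 days, and the reader cannot tell how their days were counted or whether they were included.
- The measure reported is not the one listed.

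**Working it through.** **Inputs.** Arm sizes: "81 were recruited – 50 to the acupuncture arm and 31 to the SOC arm". Drug-free days: median 7 (0-7) in each arm, p=0.253 (Secondary endpoints). Early leavers: 14 of 50 and 8 of 31 (Baseline patient data). Test for non-normal variables: Mann-Whitney (Statistical methods).

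**Can the plan's figure be reproduced?** No. Mann-Whitney needs the full distribution, and two identical medians and ranges do not supply it. The checks below ask what the printed figures allow.

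**1. Ceiling.** With a maximum of 7, a median of 7 requires:
- n=50: the 25th and 26th ordered values both equal 7, so at least 26 patients score 7 and at most 24 score less.
- n=31: the 16th ordered value equals 7, so at least 16 patients score 7 and at most 15 score less.

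The medians alone therefore bound any-use at 24/50 and 15/31 (48% each). This treats a score below 7 as meaning some drug use, which itself depends on how early leavers were scored.

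**2. Differences compatible with the p-value.** The documents give no rate of use, so I listed every any-use table with at most 24/50 and 15/31 users and a Pearson chi-square p within 0.02 of 0.253, with Newcombe 95% intervals. Differences are acupuncture minus SOC, in percentage points.

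| Users, acupuncture /50 | Users, SOC /31 | Overall use | p | Difference | 95% interval |
|---|---|---|---|---|---|
| 2 | 0 | 2% | 0.260 | +4.0 | -7.4 to +13.5 |
| 5 | 1 | 7% | 0.258 | +6.8 | -7.4 to +18.4 |
| 4 | 5 | 11% | 0.258 | -8.1 | -25.3 to +6.0 |
| 9 | 9 | 22% | 0.246 | -11.0 | -30.4 to +7.2 |
| 12 | 11 | 28% | 0.265 | -11.5 | -31.6 to +8.2 |
| 19 | 8 | 33% | 0.258 | +12.2 | -9.1 to +30.6 |
| 15 | 13 | 35% | 0.272 | -11.9 | -32.4 to +8.8 |
| 16 | 14 | 37% | 0.233 | -13.2 | -33.6 to +8.0 |
| 21 | 9 | 37% | 0.240 | +13.0 | -8.7 to +31.9 |
| 18 | 15 | 41% | 0.270 | -12.4 | -32.9 to +9.1 |
| 24 | 11 | 43% | 0.269 | +12.5 | -9.5 to +32.2 |

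Apart from the nearly empty first row, differences run from about 7 to 13 points. Where overall use is 22% or more, the wider limit is 30 to 34 points. At lower use it is 14 to 25 points.

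Hand check at an assumed 30% overall use: z=1.143 for p=0.253; SE = sqrt(0.3 × 0.7 × (1/50 + 1/31)) = 0.105; difference = 1.143 × 0.105 = 0.12; 95% interval = 0.12 ± 1.96 × 0.105 = -0.09 to +0.33.

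Because the printed p-value is presumably Mann-Whitney on days, a second check simulated 0-7 day counts with median 7 (0-7) in both arms and Mann-Whitney p within 0.01 of 0.253. Any-use differences were 5 to 19 points, and mean differences ran from 0 to about 1 day.

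**3. Power of the comparison.** For a 20-point difference in any use with 50 and 31 patients, power is 62% (10% vs 30%), 50% (20% vs 40%) and 44% (30% vs 50%). These base rates are assumed.

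**4. Early leavers.** 14 + 8 = 22 of 81 (27%), leaving 36 and 23 completers.
- If no early leaver could score 7, the medians need 26/36 (72%) and 16/23 (70%) of completers at 7.
- If every early leaver was scored 7, they need 26 - 14 = 12 of 36 (33%) and 16 - 8 = 8 of 23 (35%).

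Both are possible, so the medians do not reveal the rule. Nor can the denominator be assumed to be 50 and 31: the CAM-S severity counts in the same section sum to 11+6+9+19 = 45 and 3+0+1+24 = 28.

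**The case against.** The strongest reply is that the comparison does not rest on the medians. Mann-Whitney ranks every patient, including those below 7, so the ceiling reduces sensitivity without emptying the test. Early departure was nearly equal (28% and 26%), so no scoring rule creates an obvious imbalance. Baseline psychotropics were balanced (p=0.66), and the Cox model adjusts for number of psychotropic drugs.

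The point about the test stands, and it limits the size of the claim. A reader might infer from the ceiling that use as unequal as 48% and 16% could lie behind these medians. The medians alone allow it, but 24/50 against 5/31 gives chi-square p=0.004, so the reported p=0.253 rules that example out.

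A reader might also infer that drug-free days contradict the baseline count. They do not. A baseline median of 1 means at least 25 of 50 and 16 of 31 users; the forced overlap with patients at 7 free days is 25 + 26 - 50 = 1 and 16 + 16 - 31 = 1 (2 in the acupuncture arm if both middle baseline values are 1). One or two baseline users with no recorded drug on study days, or a different drug definition, would reconcile the figures. It is a question of definition.

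Nor do the documents say that early leavers were counted out of 7. They may have been excluded, carried forward or scored another way. The supportable point is that the rule and denominator are missing.

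The baseline balance and Cox covariate do not fill the gap, because neither is shown to capture drugs given during follow-up. Near-equal departure is reassuring about gross bias but does not make the count interpretable.

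**Conclusion.** The concern holds as a gap in evidence. The statement that psychotropic use was similar is not supported, because it rests on a ceiling-bound measure and p=0.253, with no estimate, interval or margin. If overall use was about 22% to 43%, any-use differences of 11 to 13 points in either direction fit that p-value, with 95% limits of 30 to 34 points; if use was rarer, the limits are narrower. These figures assume the base rates and treat the p-value as if it came from an any-use table. No corrected p-value can be computed without patient-level data.

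Two further defects need no assumption: no scoring rule or denominator is stated for 22 of 81 patients, and the listed antipsychotic-day outcome is not reported.

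A reader should not conclude that drug use differed, or that it explains the remission result. The documents show neither. They show that the stated safeguard, as reported, cannot settle the question.

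**What to change.** From the existing daily chart review, report for each arm:

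1. the number of patients with any use on an observed inpatient day, with the risk difference and its 95% interval;
2. drug-days per observed inpatient day, excluding days after death or discharge.

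Give both for antipsychotics (the listed outcome) and for all psychotropics, with denominators. State how early leavers were handled in the published count. Replace *similar* with the estimate and its interval. State whether the Table 1 count uses the same drug definition as the in-trial measure. Separate drugs continued from baseline and drugs newly started only if that was recorded; the documents do not show that it was.

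The cost is mainly re-tabulation. The Outcomes section ties the chart review to antipsychotic days, and the Methods say that psychotropic use was documented, but availability by day for all psychotropics should be confirmed. The downside is that the interval will be wide and the claim of equal background treatment will be weaker.

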1. *Delirium severity:* Comparison of the sum of long CAM-severity (CAM-S) score from day 2 (before treatment in the second day of the study) until day 7 (last day of evaluation). The CAM-S tool includes 10 delirium-related items, the first one being rated on a 0-1 scale and the nine followings in a 0-2 scale for a total score ranging from 0-19. The items include the four CAM items described earlier in addition to disorientation, memory impairment, perceptual disturbances, psychomotor agitation, psychomotor retardation and altered sleep-wake cycle. The sum of long CAM-S score has been shown to best reflect both 30-day and 90-day post-hospital outcomes in patients with delirium.
2. *Number of days an antipsychotic drug was administered:* as mentioned in the daily study investigator chart review.
3. *Pain:* based on twice daily Visual Analogue Scale (VAS) scores for communicating patients and FRAAC (Facial expression, Respiration, Activity, Audibility, Cry and consolability) scores for non-communicating patients. Both scales are rated on a 0-10 score and are comparable in terms of pain severity. They were routinely recorded twice daily by registered nurses.
4. *Sleep quality:* as assessed by the tenth CAM-S item.
5. *Delirium complications:* daily evaluation of falls, pulling-out intravenous or urinary catheters, new or increase in pressure ulcers grade.
6. *Length of hospital stay*
7. *Functional status at discharge:* based on Katz ADL at discharge as evaluated by study investigators.
8. *Safety and adverse events:* A checklist with acupuncture adverse events based on the AcupAE questionnaire was adapted to our study. All adverse events were recorded and monitored daily. Acupuncture-associated adverse events were discussed by the research team and the family of patients and addressed accordingly. Severe adverse events requiring patient exclusion

from the clinical trial included pneumothorax, massive bleeding, or infection in the acupoint area requiring systemic antibiotic treatment.

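### The plan gives in-hospital death no place in length of stay or discharge Katz ADL, so similar results on these two secondary outcomes do not show equal recovery if mortality differs between arms

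*Combined protocol and SAP*

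**What the plan says.** All references are to the combined protocol and SAP.

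- **Methods, Secondary outcomes, item 6** names "Length of hospital stay" and adds nothing: no start or end point, and no rule for death.
- **Methods, Secondary outcomes, item 7** defines function "based on Katz ADL at discharge as evaluated by study investigators". It does not say what is recorded for a patient who never reaches discharge.
- **Methods, Statistical methods** assigns the Mann-Whitney test to variables that are not normally distributed. It contains the only rule that mentions death: "Patients who died or were discharged before day 7 had all subsequent days counted as the last day of evaluation". That sentence goes on to limit itself to CAM and CAM-S.
- **Results, Baseline patient data** reports early exits with deaths and discharges combined: "14 (28%) were censored (dead/discharged in the 7 days of follow-up), as compared with 8 (26%) in the SOC arm".
- **Results, Secondary endpoints** says "The duration of hospitalization was similar in the 2 study arms". The figures given in support of this are "median: 13 (2-67) days in the acupuncture arm vs 12 (2-54) in the SOC arm, p=0.945". Katz ADL is described in the same way, and its figures are "median: 2 (0-6) in the acupuncture arm vs 3.5 (0-6) in the SOC arm, p=0.945". Neither line has a denominator, and the text gives no deaths by arm.

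**The concern.** Both outcomes run to the end of the admission, which lasted up to 67 days, in patients with a mean age of 84-85 and a median Charlson index of 7. Death is explicitly one of the ways out of follow-up. It is the worst result a patient can have, yet neither outcome can register it as such.

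- **Length of stay.** If a patient who dies stays in the rank comparison, the stay is shorter than it would have been had the patient lived to discharge. A shorter stay reads as better.
- **Discharge ADL.** If a patient who dies has no score, the comparison is among survivors, and the two sets of survivors need not be comparable.

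If mortality differs between arms, both effects work against seeing it. The arm with more deaths tends to show shorter stays. If its frailest patients are the ones who die, it also tends to show better function in those who remain. What is at stake is the meaning of two null secondary results.

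**Working it through.** **1. What the printed figures allow.** Early exits are 14/50 = 28% and 8/31 = 25.8%. The uncorrected chi-square is 81 × (14×23 − 36×8)² / (50×31×22×59) = 81 × 34² / 2,011,900 = 0.047, p = 0.83. With continuity correction, or by Fisher's exact test, p = 1.0. The document prints p = 0.87, which does not reproduce exactly, but the conclusion is the same. The p-values for length of stay and ADL cannot be recomputed from medians and ranges.

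**2. Merged exits say nothing about deaths.** The 14 and 8 can be split in any way:

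| Deaths by day 7, acupuncture vs SOC | Rates | Fisher p |
|---|---|---|
| 14 vs 0 | 28% vs 0% | 0.0006 |
| 7 vs 4 | 14% vs 13% | 1.0 |
| 0 vs 8 | 0% vs 26% | 0.0002 |

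The count also stops at day 7, while median stays are 13 and 12 days, so later in-hospital deaths lie outside it.

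**3. Denominators cannot be taken for granted.** In the neighbouring CAM-S result, the severity counts sum to 11+6+9+19 = 45 of 50 and 3+0+1+24 = 28 of 31. So 5 and 3 patients are absent without explanation.

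**4. Length of stay, by simulation.** Deaths by arm are not in the visible text, so mortality is assumed. The set-up is 50 vs 31 patients with the same underlying stay in both arms (log-normal, median 12.5 days, log-SD 0.75). Death falls uniformly between 10% and 100% of the would-be stay. The Mann-Whitney test is applied to the observed stay, then again with death ranked as the longest stay. Ranges cover repeated runs of 1,500 to 3,000 trials.

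| Assumed mortality | Higher-mortality arm has shorter-ranked stay, deaths kept | Same arm shown as worse, death ranked worst | p<0.05, deaths kept | p<0.05, death ranked worst |
|---|---|---|---|---|
| Equal | about 50% | about 50% | about 5% | about 5% |
| 15% vs 10% | 56% | 66% | 5% | 7% |
| 20% vs 10% | 62-65% | 78-83% | 6% | 10-11% |
| 30% vs 10% | 76-77% | 94-97% | about 11% | about 31% |

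The benchmark for the two direction columns is 50%.

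**5. Discharge ADL, by simulation.** This separate run used 3,000 trials, stays with median 13 days and log-SD 0.8, and the same ADL distribution in both arms, unrelated to death. At 28% vs 10% mortality, survivors-only ADL is significant in 4% of trials, against 25% with death ranked worst. At the extreme of 28% vs 0% the figures are 5% and 57%. Because ADL was drawn independently of death, this shows that the survivors-only comparison does not see mortality. It does not measure the further distortion that would arise if frailer patients die.

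**The case against.** The strongest reply has four parts.

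- **Handling is unstated, so the bias is not shown.** A reader might infer that deaths were in fact entered as short stays and dropped from ADL. The documents do not say so. Deaths could have been excluded from length of stay, or scored 0 on Katz. Nor is a death necessarily a short stay: a late death ends a long one. This stands. What can be said is that the plan has no rule and that the default handling is unsatisfactory.
- **No survival difference is shown.** A reader might infer that the wording hides worse survival in one arm. Nothing in the visible text supports that in either direction. Figure 1, the flow diagram, was not visible in the copy reviewed and may give deaths and analysed numbers. This also stands, although a flow diagram would not supply the missing analysis rule.
- **The size is modest.** At 20% vs 10% mortality, a non-significant result stays non-significant in roughly 90% of trials even with death ranked worst. This stands. The change is substantial only when the mortality difference is large.
- **The remedies target different quantities, and the outcomes are secondary.** Time to live discharge, death as the longest stay and death below Katz 0 are different estimands, and the last two place a value on death. This is a fair reason to present the ADL composite only as a sensitivity analysis. It does not excuse leaving the handling undefined.

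**Conclusion.** The point holds as a gap in the analysis plan with a conditional consequence. Neither outcome accommodates in-hospital death, and the one rule that mentions death does not reach them. If mortality differs between arms, *similar* on length of stay and discharge ADL does not show equal recovery. If mortality is equal, the length-of-stay analyses agree and little changes.

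The size depends entirely on assumed mortality and on when deaths occur. At 20% vs 10% the ranking tilts in favour of the worse arm, but few significance calls change. At 30% vs 10% significance moves from about 11% to about 31%. None of these figures estimates what happened in this trial.

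The ADL medians of 2 vs 3.5 should not be read as evidence of a hidden survival effect, since neither the denominators nor the handling of deaths is known. They do carry the same p=0.945 as length of stay, which may be a copying error and should be checked. The primary delirium result does not depend on this point.

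**What to change.** 1. Define length of stay as time to discharge alive, with in-hospital death as a competing event, and present the cumulative incidence of live discharge by arm.
2. Report in-hospital deaths over the whole admission by arm, separate from discharges, and the number analysed per arm for both outcomes. If Figure 1 already gives some of this, refer to it in the text.
3. Keep the survivors-only ADL medians as description, and add a sensitivity analysis with death ranked below the lowest Katz score.
4. Replace *similar* with the between-arm estimate and its 95% CI for each outcome, and check the repeated p-value while doing so.

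The cost is a small re-analysis of data that should already be in the hospital record, with no new collection. The drawback is that an ADL ranking that includes death is harder to interpret than a median score, which is why it belongs beside the descriptive result and should not replace it.
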